3 OBJECTIVES AND ENDPOINTS

Table 4 Objectives and Endpoints

Objectives	Endpoints
Primary	

 To evaluate the efficacy of triptorelin pamoate 22.5 mg 6-month formulation in achieving castrate levels of testosterone To evaluate the efficacy of triptorelin pamoate 22.5 mg 6-month formulation in maintaining the castrate levels of serum testosterone 	
 Percentage of participants achieving castrate levels of serum testosterone (<50 ng/dL or 1.735 nmol/L) on Day 29 Percentage of participants maintaining the castrate levels from Week 8 to Week 24
Secondary	

 To assess the safety profile including local tolerability of triptorelin pamoate 22.5 mg 6-month formulation 	
 Incidence of TEAEs (including local tolerability) throughout the study i.e., up to Week 24 Change from baseline in clinical safety laboratory parameters (blood chemistry and haematology) at Week 24 Change from baseline in physical examination at Day 1, Week 12 and Week 24 Change from baseline in ECG at Week 4 and Week 24 Change from baseline in vital signs (blood pressure and heart rate) at each visit up to Week 24

 To demonstrate the effect of triptorelin pamoate 22.5 mg 6-month formulation on PSA response 	
 Percent change in PSA from baseline (prior to injection) at Week 12 and Week 24 (percent change in PSA is defined as the absolute value of difference between the PSA values at Week 12 and Week 24 and the baseline value divided by the baseline value)

 To assess the PK of triptorelin pamoate 22.5 mg 6-month formulation in a subset of 12 participants 	
 PK parameters for dosing interval up to 24 weeks: 
 t_{max} C_{max} AUC_{0-169} AUC_{last}

 To assess the PD of testosterone in a subset of 12 participants 	
 PD parameters for dosing interval up to 24 weeks: 
 t_{max} C_{max} t_{cast}

 To assess the PK of triptorelin pamoate 22.5 mg 6-month formulation for all participants 	
 Sparse plasma concentrations of triptorelin at pre-dose and post-dose at Weeks 4, 8, 12, 16, 20 and 24

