2 PROTOCOL OVERVIEW

2.1 Study Objectives and Hypotheses

The primary objectives of the study are:

- To evaluate the efficacy of triptorelin pamoate 22.5 mg 6-month formulation in achieving castrate levels of testosterone
- To evaluate the efficacy of triptorelin pamoate 22.5 mg 6-month formulation in maintaining the castrate levels of serum testosterone

The secondary objectives are:

- To assess the safety profile including local tolerability of triptorelin pamoate 22.5 mg 6-month formulation
- To demonstrate the effect of triptorelin pamoate 22.5 mg 6-month formulation on prostate-specific antigen (PSA) response
- To assess the PK of triptorelin pamoate 22.5 mg 6-month formulation in a subset of 12 participants with rich PK sampling schedule
- To assess the PD of testosterone in a subset of 12 participants with rich PD sampling
- To assess the PK of triptorelin pamoate 22.5 mg 6-month formulation for all participants
- To assess the PD of testosterone for all participants

The exploratory objective is:

- To evaluate the PK/PD relationship between the PK of triptorelin pamoate 22.5 mg 6-month formulation and testosterone concentration versus time profiles

No statistical hypotheses are planned for this study.

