Local tolerance will be assessed 2 hours (± 15 minutes) after the single injection of 6-month formulation triptorelin, the injection site will be examined including but not limited to tenderness, erythema, swelling, haematoma, rash, pain, itching and induration. The presence of local tolerance will be listed and summarized for each symptom. The maximum length (mm) and width (mm) of presented symptom will also be summarized where applicable.

5.9 PK

5.9.1 *Triptorelin Plasma Concentrations*

Tables, listings and figures of triptorelin plasma concentrations will be generated by the SP for both the Rich PK Analysis Set and the Population PK Analysis Set.

Individual plasma concentrations of triptorelin will be listed and summarised by visit and time points using descriptive statistics for continuous variables including number of available observations (n), mean, median, SD, minimum, maximum, SEM, CV, geometric mean, geometric coefficient of variation (gCV) % (assuming log normally distributed data, and calculated as: $gCV\% = \text{SQRT}(e^{s^2}-1)*100$; where s is the SD of the log-transformed values) and 95% CI for mean.

Plasma concentrations should be displayed with the same precision than the LLOQ. In descriptive statistics, calculations derived from plasma concentrations (mean, minimum, maximum, median, SD etc.) should follow the same rule whereas CV% will only be displayed with one decimal digit.

Source data as reported from the laboratory will be used for calculation of concentration summary statistics. All values below or above a limit of detection (e.g. <0.1 or >100) will be listed as such. LLOQ will be presented as 'BLQ' in the listings and the LLOQ value presented as a footnote. Missing PK samples will be reported as no sample (NS) and/or not reportable (NR) and considered excluded from plasma concentration summary statistics. For summary tables, all BLQs will be considered as missing and will not be included in the summary statistics. The number of BLQs and non-BLQs at each scheduled time point will be reported. Summary Statistics will not be calculated if non-BLQ concentrations at a scheduled time point is less than 3 and if more than one third (1 out of every 3 values) are missing; in that case only minimum and maximum will be reported. Individual and mean triptorelin concentration time profiles, as well as spaghetti plots, will be generated.

5.9.2 *Triptorelin PK Analysis*

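### Read literally, the 'and if' in SAP 5.9.1 leaves the one-third limit on concentration statistics with no effect, so a mean and 95% CI can be printed from 3 quantifiable values out of 12 or 195.

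*SAP*

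**What the plan says.** SAP 5.9.1 (Triptorelin Plasma Concentrations) provides for tables "for both the Rich PK Analysis Set and the Population PK Analysis Set". The statistics by visit and time point include the mean, SD, SEM, geometric mean, geometric CV and a 95% CI for the mean. Four rules govern incomplete data:

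- Samples not taken or not reportable: "Missing PK samples will be reported as no sample (NS) and/or not reportable (NR) and considered excluded from plasma concentration summary statistics".
- BLQ values: "For summary tables, all BLQs will be considered as missing and will not be included in the summary statistics".
- Disclosure: "The number of BLQs and non-BLQs at each scheduled time point will be reported".
- Withholding: "Summary Statistics will not be calculated if non-BLQ concentrations at a scheduled time point is less than 3 and if more than one third", with the sentence continuing "1 out of every 3 values) are missing; in that case only minimum and maximum will be reported".

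SAP 5.11.1 applies the same conditions to testosterone serum concentrations in the FAS and the Rich PD Analysis Set. Protocol 9.4.3.2 lists the descriptive statistics but gives no withholding rule, so nothing elsewhere settles how the two conditions are to be joined.

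**The concern.** The withholding rule is there to stop a time point being summarised when too little of it is quantifiable. It names two limits, a minimum count of 3 and a maximum missing share of one third. Joined by 'and', both must be breached before anything is withheld. If breaching the first always breaches the second, the second limit is only decoration, and the protection is much weaker than a reader of the SAP would suppose.

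By-visit triptorelin and testosterone concentrations for all participants are secondary endpoints (Protocol section 3, Table 4). If many values at a visit were BLQ, the table could show a mean and CI describing only the upper part of the distribution. For testosterone, low values are the intended drug effect, so BLQ results are plausible there.

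**Working it through.** **Inputs.** Rich-sampling subset: 12 (SAP 2.1). All participants: 195 planned (SAP 2.2). The plan's own figure reproduces: 165 / (1 − 0.15) = 194.1, rounded up to 195 (SAP 2.3). The limits of 3 values and one third come from SAP 5.9.1. They are rules, so there is no stated result to recompute.

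**Step 1: does the first condition imply the second?** Let N be the number of participants at a time point and q the number of non-BLQ values. With BLQ counted as missing, the missing share is (N − q)/N. If q ≤ 2, this share is at least (N − 2)/N.

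- N = 4: 2/4 = 50%, above one third.
- N = 12: 10/12 = 83.3%.
- N = 195: 193/195 = 99.0%.

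(N − 2)/N rises with N, so it exceeds one third for every N ≥ 4. Checking every pair (N, q) for N = 1 to 195, the 'and' rule differs from q < 3 alone only at (1,1), (2,2) and (3,2). For N ≥ 4 the rule is simply 'fewer than 3 quantifiable values'.

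**Step 2: smallest q at which statistics are printed.**

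| N | 'and' as written | 'or' | Values of q where they differ |
|---|---|---|---|
| 12 | 3 (9/12 = 75.0% missing) | 8 (4/12 = 33.3% missing) | 3 to 7 |
| 195 | 3 (192/195 = 98.5% missing) | 130 (65/195 = 33.3% missing) | 3 to 129 |

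The two connectors agree whenever one third or fewer are missing, and whenever q < 3.

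**Step 3: size of the effect on a printed mean.** The documents give no LLOQ, BLQ rate or variability, so this step is illustration only. Assume log-normal concentrations, no samples missing for other reasons, and a quantifiable fraction f. With s = √ln(1 + gCV²) and z = Φ⁻¹(1 − f), the mean of the quantifiable values divided by the true mean is Φ(s − z)/f.

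- Half BLQ (f = 0.50, z = 0): gCV 50% gives s = 0.472 and a ratio of 1.36; gCV 80% gives s = 0.703 and a ratio of 1.52.
- 75% BLQ (f = 0.25, z = 0.674): 1.68 at gCV 50% and 2.05 at gCV 80%. At a lower gCV of 30% the ratio is 1.41.

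**Step 4: the denominator matters once 'or' is used.** Suppose 165 of 195 participants remain at Week 24 and 36 of their samples are BLQ, so 129/165 = 78% are quantifiable. If the 30 dropouts count as missing, the missing share is (30 + 36)/195 = 33.8%, and all statistics would be suppressed. With reportable samples as the denominator, the share is 36/165 = 21.8%, and they are printed.

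**The case against.** **The wording may be loose rather than wrong.** The second 'if' could introduce a separate ground for withholding, which would amount to 'or'. That is possible, and it is why the conclusion is confined to the literal reading. A programmer still has to choose, and the choice changes the output for q = 3 to 7 of 12 and q = 3 to 129 of 195.

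**'Missing' might mean only samples not taken or not reportable.** The paragraph does also use the word that way. The one-third clause would then operate, but only to weaken the guard: 2 quantifiable and 10 BLQ values out of 12 would be summarised. The sentence on BLQ values in summary tables points the other way.

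**Readers are not left blind.** This stands. BLQ and non-BLQ counts are reported at each time point, individual values are listed, the LLOQ is footnoted and spaghetti plots are produced. A mean from 3 of 12 would appear beside 9 BLQ.

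**Heavy BLQ may never occur.** This also stands. The product is described as releasing drug over 169 days (Protocol 4.3), and 192 of 195 BLQ is a logical extreme, not a forecast.

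**Stronger conclusions a reader might infer.** A reader might conclude that the rich-subset PK results or comparisons with historical data are biased. The documents do not support that. The subset objective ("To assess the PK of triptorelin pamoate 22.5 mg 6-month formulation in a subset of 12 participants") has tmax, Cmax and AUC as its endpoints, derived by non-compartmental analysis under a separate plan. Protocol 9.4.3.2 places historical comparison within population PK modelling, also under its own plan. A reader might also blame the connector for two further effects: inflation of the mean at exactly one third BLQ, and a reported minimum that cannot fall below the LLOQ. Both come from dropping BLQ values and would remain under 'or'.

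**Conclusion.** The point holds for the rule as literally written. With BLQ counted as missing, the one-third limit has no effect at any time point with 4 or more participants, and this is exact. Three quantifiable values are enough to print a mean, SEM, geometric mean and 95% CI, whether from 12 or from 195. The documents do not show whether 'or' was intended.

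The consequence is limited to descriptive by-visit concentration tables for triptorelin and, through SAP 5.11.1, testosterone. The non-compartmental, population PK and co-primary results are not shown to depend on it. SAP 5.7.2.2 handles BLQ testosterone in the efficacy summary by a different rule, substituting the LLOQ. The inflation figures rest on the assumed log-normal shape and gCV; if one third or fewer of the values are BLQ, the connector makes no difference. It merits correction because a prespecified safeguard on secondary-endpoint tables cannot work as stated and the repair is cheap.

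**What to change.** In SAP 5.9.1, replace 'and if' with 'or if', and define the denominator as samples collected and reportable at that time point: BLQ counted, samples not taken or not reportable and dropouts not counted. Suggested wording:

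> Statistics are withheld at a time point when fewer than 3 concentrations are non-BLQ, or when more than one third of the reportable samples there are BLQ. In that case only the numbers of BLQ and non-BLQ values, the minimum and the maximum are shown.

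Apply the same wording to testosterone through SAP 5.11.1. If the one-third limit is not wanted, delete it so that the text matches what the program will do.

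The cost is one connector, one definition and one condition in the table program. The downside is that some time points may show only counts, minimum and maximum; restricting the denominator to reportable samples keeps dropout alone from causing that.

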5.10 Anti-drug Antibodies

Not applicable.

5.11 PD

5.11.1 *Testosterone Serum Concentrations*

Tables, listings and figures of testosterone serum concentrations will be generated by the SP for both the FAS and the Rich PD Analysis Set, following the same conditions described in 5.9.1 for triptorelin plasma concentrations.

5.11.2 *Testosterone PD Analysis*

The PD analyses of testosterone serum concentrations for the Rich PD Analyses Set will be performed by NCA. The NCA analysis will be described in a separate analysis plan and reported in a standalone report.

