
 To assess the PD of testosterone for all participants 	
 Sparse serum concentrations of testosterone at pre-dose and post-dose at Weeks 4, 8, 12, 16, 20 and 24
Exploratory	

 To evaluate the PK/PD relationship between the PK of triptorelin pamoate 22.5 mg 6-month formulation and testosterone concentration versus time profiles (PD) 	

AUC_{0-169} =area under the plasma concentration time curve from time 0 to the visit on Day 169; AUC_{last} =area under the plasma concentration time curve from time 0 to the last quantifiable concentration; C_{max} =maximum concentration;

ECG=electrocardiogram; PD=pharmacodynamics; PK=pharmacokinetics; PSA=prostate specific antigen; t_{castr} =time to castration; TEAE=treatment-emergent adverse event; t_{max} =time to peak serum/plasma concentration

Note: A list of laboratory parameters to be assessed during the study are presented in Appendix 10.2.

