- (d) Missing data between two visits where castration levels are maintained will be handled as missing for that particular visit, and the participant will be considered to have maintained castration.

To derive the percentage of participants maintaining castrate levels of testosterone, assessable participants are defined as the total number of all participants having values at all visits and all participants having missing data according to the criteria a), c) and d) mentioned previously. Participants having missing data according to the criteria b) will be excluded from this calculation.

Co-primary endpoints will be tabulated with two-sided 95% (95% CI) using the Clopper-Pearson exact method.

9.4.3 *Analysis of Secondary Endpoints*

9.4.3.1 *Prostate-Specific Antigen*

The secondary efficacy variable is the percent change in PSA from baseline (prior to injection) measured at Week 12 and Week 24. Percent change in PSA is defined as the absolute value of difference between the PSA values at Week 12 and Week 24 and the baseline value divided by the baseline value.

PSA percent change from pre-treatment Day 1 will be reported at each subsequent visit, using descriptive statistics.

9.4.3.2 *Pharmacokinetic and Pharmacodynamic Data Analysis*

Description of Triptorelin and Testosterone Concentrations

Individual plasma or serum concentrations of triptorelin and testosterone will be listed and summarised by visit and time points using descriptive statistics for continuous variables (number of available observations, mean, median, SD, minimum, maximum, geometric mean, and geometric coefficient of variation (assuming log normally distributed data). Data will be

summarised for the PK/PD subset and overall. Individual and mean triptorelin and testosterone concentration time profiles, as well as spaghetti plots, will be generated.

Non-compartmental Analysis

The PK analysis of triptorelin plasma concentrations and testosterone serum concentrations of the rich sampling PK/PD subset will be performed by the non-compartmental analysis (NCA) approach using Phoenix WinNonlin PK program version 8.3 or higher. The following PK parameters will be calculated if warranted by the data:

- maximum observed concentration (C_{\max})
- time to maximum observed blood concentration (t_{\max})
- (for triptorelin only) area under the plasma concentration time curve from time 0 to the time of the last quantifiable concentration (AUC_{last})

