4 ANALYSIS SETS

Screened Set

The screened set will contain all participants screened (i.e. who signed the informed consent).

Full Analysis Set (FAS)

The FAS will contain all treated participants who complete the study or is a treatment failure. Completing the study is defined as having serum testosterone measurement at baseline, Day 29 and Day 169. Treatment failure is defined as escaping castration (testosterone level ≥ 50 ng/dL or 1.735 nmol/L) at any assessments on and after Day 29 during the study, or premature discontinuation from the intervention period due to drug-related reasons (adverse event or death).

Per Protocol Set (PPS)

The PPS will contain all participants in the FAS who have no impacting major protocol deviations (i.e. that could potentially affect the primary efficacy endpoint outcome for the participant) as described in the protocol deviations document.

Safety Set

The safety set will contain all participants who receive the single dose of study intervention.

Rich PK Analysis Set (for non-compartmental analysis)

The rich PK analysis set will contain all participants in the PK/PD subset who receive one dose of study intervention, have no major protocol deviations affecting the PK variables, and who have a sufficient number of plasma concentrations to estimate the main PK parameters (maximum observed plasma drug concentration (C_{max}), time to maximum observed drug concentration (t_{max}) and area under the plasma concentration time curve (AUC)).

The criteria of major protocol deviations affecting the PK variables will be defined in the protocol deviation document. The process to review major protocol deviations potential impact on PK parameters will be ongoing and the final Rich PK Analysis Set will be determined during data review meeting.

Population PK Analysis Set

The population PK analysis set will contain all participants who received one dose of triptorelin and who have at least one triptorelin plasma concentration and no major protocol deviations affecting PK variables.

Rich PD Analysis Set

The rich PD analysis set will contain all participants in the PK/PD subset who have a sufficient number of PD (testosterone) measurements to estimate the main PD parameters (maximum observed concentration (C_{max}), time to maximum observed concentration (t_{max}) and time to castration (t_{castr})).

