5.7.3 Analysis of Key Secondary Efficacy Endpoints

5.7.3.1 Endpoint, Treatment Effect and Estimand Definition

The secondary efficacy variable is the percent change in PSA from baseline (prior to injection) measured at Week 12 and Week 24. Percent change in PSA is defined as the value of difference between the PSA values at Week 12 and Week 24 and the baseline value divided by the baseline value.

$$\text{Percent change from baseline (\%)} = \left(\frac{\text{PSA value at Week 12 or Week 24} - \text{Baseline value}}{\text{Baseline value}} \right) \times 100$$

5.7.3.2 *Main Secondary Analysis*

PSA percent change from Baseline will be reported at each subsequent visit, using descriptive statistics on the FAS and PPS.

Observed value will also be summarized for the FAS. Descriptive statistics to be presented include number of available observations (n), mean, median, SD, minimum, maximum, standard error mean (SEM, calculated as SD divided by the square root of n), coefficient of variation (CV) and 95% CI for mean.

Individual PSA level data versus visit will be plotted by participant on a semi-logarithmic scale on the FAS. The arithmetic mean (\pm SD) PSA levels versus visit will also be provided.

All PSA data will be listed by participant and timepoint on all participants enrolled.

5.7.3.3 *Subgroup Analysis*

No subgroup analyses will be performed.

5.7.4 *Analysis of Other Secondary Efficacy Endpoints*

Not applicable.

5.7.5 *Analysis of Exploratory Endpoints*

An exploratory endpoint is defined in Protocol, but the analysis details will be described in a separate data analysis plan.

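### The testosterone PD objective covers all participants, but SAP 5.11.1 tabulates it on the FAS, which leaves out men according to outcome and completion

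*SAP*

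**What the plan says.** **Objective and endpoint.** Protocol section 3 (Table 4) sets a secondary objective, "To assess the PD of testosterone for all participants", with the endpoint "Sparse serum concentrations of testosterone at pre-dose and post-dose at Weeks 4, 8, 12, 16, 20 and 24". SAP 2.1 repeats the objective. Protocol 9.4.3.2 says triptorelin and testosterone concentrations will be "summarised for the PK/PD subset and overall".

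**Analysis set for testosterone.** SAP 5.11.1 states that the tables, listings and figures "will be generated by the SP for both the FAS and the Rich PD Analysis Set".

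**What the FAS is.** SAP 4: "The FAS will contain all treated participants who complete the study or is a treatment failure". And: "Completing the study is defined as having serum testosterone measurement at baseline, Day 29 and Day 169". A treatment failure is a man at or above 50 ng/dL at any assessment from Day 29 on, or one who stops early because of a drug-related adverse event or death.

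**Analysis set for triptorelin.** SAP 5.9.1 reports plasma concentrations "for both the Rich PK Analysis Set and the Population PK Analysis Set". The Population PK set needs one dose, at least one concentration and no major deviation affecting PK. It has no completion condition.

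**PSA.** SAP 5.7.3.2: "PSA percent change from Baseline will be reported at each subsequent visit, using descriptive statistics on the FAS and PPS". Protocol 9.3 itself assigns secondary efficacy endpoints to the FAS and PP set.

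SAP 2.6, the list of changes from the protocol's statistical section, has a single entry. It concerns medical history and medications.

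**The concern.** A by-visit concentration summary needs only a value at that visit. Requiring a Day 169 value as well removes earlier results that were validly measured, and it does so according to outcome. Take two men who leave at Week 16 for the same non-drug-related reason. If one has escaped castration, all his values stay in. If the other is still castrate, his pre-dose, Week 4, Week 8 and Week 12 values all leave the FAS tables and figures. A man who finishes without escaping but missed one of the three required samples is lost in the same way.

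Two things are at stake. A stated secondary endpoint is not summarised on its stated population. And the triptorelin and testosterone tables, which a reader will set side by side given the exploratory PK/PD objective, rest on different men.

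**Working it through.** **The plan's own figures.** With 165 men, a null of 85% and two-sided 0.05, the upper rejection limit is 150 or more successes. Power at 93% is 0.8832, which matches the stated 88.3%. Inflation for dropout: 165 / (1 − 0.15) = 194.1, rounded up to 195. These figures only supply planning rates here: 195 men, 15% dropout, 97.5% castrate at Day 29 and 93% maintained.

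**Who is in which summary**

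| Treated man | FAS (testosterone, 5.11.1) | Population PK set (triptorelin, 5.9.1)* |
|---|---|---|
| Has baseline, Day 29 and Day 169 values | in | in |
| Escapes, then leaves | in | in |
| Castrate, leaves for a drug-related AE or death | in | in |
| Castrate, leaves for another reason, no Day 169 value | **out** | in |
| Finishes without escaping, one of the three samples missing | **out** | in |

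*Given at least one concentration and no major PK deviation.

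**Values lost from the summaries.** Assumptions: all 15% leave for non-drug-related reasons, evenly over 24 weeks, and at most 7% of leavers escape first. Leavers: 195 × 0.15 = 29.25.

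- Week 4: leavers still present, 29.25 × 20/24 = 24.4. Values measured, 195 − 29.25 × 4/24 = 190.1. Lost: between 24.4 × 0.93 = 22.7 and 24.4, so about 23 of 190 (12%).
- Week 12: leavers still present, 29.25 × 12/24 = 14.6. Values measured, 195 − 14.6 = 180.4. Lost: between 14.6 × 0.93 = 13.6 and 14.6, so about 14 of 180 (8%).

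**Range.** With d the non-drug-related dropout and D the total dropout, the share lost at week w is 0.93 × d(1 − w/24) / (1 − D·w/24).

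| Case | Week 4 | Week 12 |
|---|---|---|
| D = d = 5% | 3.9% | 2.4% |
| D = d = 15% | 11.9% | 7.5% |
| D = d = 20% | 16.0% | 10.3% |
| D = 15%, half drug-related (d = 7.5%) | 6.0% | 3.8% |

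**Effect on the summaries.** The documents give no testosterone means, so the levels below are assumed.

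- Week 12: suppose half of the 7% have escaped by then (3.5%). After removing 14 of 180 values, the escaper share is 3.5% × 180/166 = 3.8%. With levels of 10 (castrate) and 100 ng/dL (escaped), the mean goes from 0.035 × 100 + 0.965 × 10 = 13.15 to 0.038 × 100 + 0.962 × 10 = 13.42. That is +0.27 ng/dL, or 2%.
- Day 29, limiting case in which every leaver goes after Day 29 and is castrate: non-castrate men number 0.025 × 195 = 4.875. With means of 10 and 75, all treated gives (190.125 × 10 + 4.875 × 75)/195 = 11.62, and the FAS gives (160.875 × 10 + 4.875 × 75)/165.75 = 11.91, a shift of +0.3. With means of 20 and 200, the mean goes from 24.50 to 25.29, a shift of +0.8. The non-castrate share goes from 2.5% to 4.875/165.75 = 2.9%.

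**The case against.** The strongest reply is that the phrase about all participants is a sampling contrast (sparse samples from everyone, rich samples from 12 men) and does not name an analysis set. Protocol 9.3 sends PK and PD to the relevant set, yet the only PD set it defines is the rich one, so the SAP had to choose something for the overall table. The Population PK set is not literally everyone either. This is fair, and it makes an undeclared departure under SAP 2.6 arguable. It does not explain why the triptorelin table, under a parallel objective, needs no Day 169 sample while the testosterone table does.

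The size also depends on programming. SAP 5.1.1.3 gives the last visit one label for end of study and early withdrawal, and SAP 6.2 says there is no remapping. If an early-withdrawal value were accepted as Day 169 for FAS membership, many leavers with baseline and Day 29 values would stay in. The plain wording of Day 169 points the other way, but the percentages are upper-end figures for a given dropout rate. In addition, 5.11.1 takes over the 5.9.1 rule that treats values below quantification as missing, so the mean shifts are only indicative.

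A reader might infer four stronger things that the documents do not support:

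- That the data are discarded. SAP 5.7.2.2 and 5.7.3.2 list testosterone and PSA for all enrolled participants. A man in the PK/PD subset can also still be in the Rich PD set.
- That every castrate man who leaves early is lost. Drug-related leavers stay in the FAS.
- That PSA contradicts the protocol. The protocol puts secondary efficacy endpoints on the FAS and PP set, and the PSA objective has no all-participants wording. A Week 12 PSA from a man who leaves castrate at Week 16 does drop out of the summary, but that is a selection weakness in a set the protocol chose.
- That the choice flatters the drug. It over-represents escapers, so suppression looks slightly worse.

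**Conclusion.** The point holds for testosterone and is minor. SAP 5.11.1 reports the all-participants testosterone endpoint on a set defined by completion or failure, and so removes measured values from the by-visit summaries according to outcome. With 15% non-drug-related dropout spread evenly, about 12% of Week 4 and 8% of Week 12 values are affected. These shares roughly halve if half of the leavers are drug-related, and they fall further if early-withdrawal values are counted as Day 169. The effect on the mean is a few tenths of a ng/dL under assumed levels, against a threshold of 50 ng/dL. The tables are descriptive, with no testing, so no conclusion would reverse. The reason to act is that the endpoint should be summarised on the population stated for it, and that the PK and PD tables should describe comparable men.

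**What to change.** - In SAP 4, define a population PD set: all treated participants with at least one post-dose testosterone value.
- In SAP 5.11.1, use it for the overall testosterone tables and figures, beside the Rich PD set. A FAS-based testosterone summary already exists under SAP 5.7.2.2, so nothing is lost.
- State that early-withdrawal values are not pooled with Day 169 in these summaries.
- For PSA, keep the FAS and PPS. Optionally add a supporting summary on all treated men with a baseline and a value at that visit.

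The cost is SAP wording, one population flag and a few tables. No new data are needed. If the FAS is kept in 5.11.1, the minimum is to declare and justify the choice in SAP 2.6.
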